9.2.10 Visit 9 (Week 26, phone call)

Twenty-six weeks after the start of study treatment the site personnel will call the patients to inquire about adverse events, including cardiovascular events, and to collect information on concomitant medications. For patients who discontinue study drug treatment early, the phone call will still be made 26 weeks after the start of study treatment. Information collected during the phone call must be recorded in the patient's medical records / source documents.

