For cases where start month and year are reported but day is missing, impute the maximum of (date of randomization, first date of study medication, 15.month.year).
For cases where only start year is reported or completely missing, impute the maximum of (date of randomization, first date of study medication, 15.01.year), but not later than death date if the subject died.
- **Heart failure related concomitant medication start date**
For case where start month and year are reported but day is missing, impute it with 15th day of month. For cases where only start year is reported or completely missing, impute it as maximum of (15.01.year, randomization).
- **Heart failure related concomitant medication stop date**

For case where stop month and year are reported but day is missing, impute it as minimum of [(15, month, year) and (last visit date) and (death date)].

If the stop day and month are missing, then the stop date will be imputed as minimum of [(15.12.year) and (last visit date) and (death date)].

If the date is completely missing then the stop date will be imputed as minimum of [the last visit date and death date]. If the concomitant medication is “Ongoing at subject's last visit”, for the respective stop date variable the ‘last visit date’ from the corresponding domain is merged in the concomitant medication database by data management programming.

- **Study medication start date for subjects took study medication**

If the start date and time is missing it will be imputed with the randomization date and time. If start date and time is recorded as earlier than randomization and cannot be clarified, date and time of randomization will be used for the statistical analysis.

- **Study medication stop date for subjects took study medication**

If the stop day is missing, but the stop month and stop year are available then the stop date will be imputed as minimum of [(15, month, year) and (last on treatment visit date before the observational visit) and (death date)].

If the stop day and month are missing or the date is completely missing then the stop date will be imputed as minimum of [the last on treatment visit date before the observational visit and death date].

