6.2.2.2 Primary analyses of secondary efficacy variables

The primary analysis of key echocardiographic parameters will be performed in PPS LVEF and other secondary efficacy variables will be performed in PPS BNP. The missing values of post baseline of LVESV and LVEDV will be imputed by WOV if the baseline values are not missing and the subjects have CV death or HF hospitalization, otherwise remains missing. Similarly The missing values of post baseline of hs-TNT will be imputed by WOV if the baseline values are not missing and the subjects have CV death or HF hospitalization, otherwise remains missing. The secondary efficacy variables, except for the clinical outcomes, will be analyzed using similar statistical methods as for the primary efficacy

variables, i.e. the MCP-Mod method with the same standardized candidate dose-response shapes (with the proper direction: decreasing trend for change of LVESV, LVEDV and log-transformed hs-TNT) and corresponding coefficients as for the primary variables.

Time to adjudicated clinical outcome event since randomization (using both separate and composite outcomes) will be described by means of Kaplan-Meier (KM) estimates by treatment group. The subjects who do not have the corresponding clinical outcomes until week 26 visit (upper time limit, i.e. 182+7days) will be considered as right-censored at the minimum of date of last visit, date of week 26 visit, study day 189, and date of death (in case death is non CV death). KM estimates for each visit will be tabulated.

Additionally time to adjudicated on-treatment clinical outcome events since randomization (using both separate and composite outcomes) will also be described up to 6 weeks after last dose in each treatment arm respectively. The subjects who do not have the corresponding clinical outcomes until 6 weeks after last dose will be considered right censored at minimum of 6 weeks after last dose, date of last visit and date of death (in case death is non CV death).

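### SAP 4.3: a clinical-outcome date known only by month can be imputed after the patient's death, and neither partial-date rule stops at the end of follow-up

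*SAP*

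**What the plan says.** SAP 4.3 has two sentences for partial clinical-outcome dates.

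- **Month and year known.** When "start month and year are reported but day is missing, impute the maximum of (date of randomization, first date of study medication, 15.month.year" applies, the result is the latest of three dates. No upper limit follows.
- **Year only, or nothing known.** The rule is to "impute the maximum of (date of randomization, first date of study medication, 15.01.year), but not later than death date if the subject died".

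The same section caps the stop date of heart failure medication when the month is known: "impute it as minimum of [(15, month, year) and (last visit date) and (death date".

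These dates feed the Kaplan-Meier analyses in SAP 6.2.2.2. Patients who "do not have the corresponding clinical outcomes until week 26 visit (upper time limit, i.e. 182+7days) will be considered as right-censored", and the date used for censoring is given as "minimum of date of last visit, date of week 26 visit, study day 189, and date of death (in case death is non CV death". A parallel on-treatment analysis ends 6 weeks after the last dose. Neither analysis says what to do with an imputed date that falls after death or after its limit.

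Protocol 9.2.10 places the last contact close to this limit: at Week 26 "the site personnel will call the patients to inquire about adverse events, including cardiovascular events". The schedule in Protocol 9.1 allows that call from Day 182 to Day 189.

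**The concern.** The words "but not later than death date if the subject died" belong only to the sentence for the less precise dates. A date known to the month therefore has less protection than one not known at all, and no reason is given.

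Two things follow. First, the separate analysis of heart failure hospitalization can contain an event dated after the patient died. Second, a patient with a real event shortly before the end of follow-up can lack an outcome by Day 189 on the imputed date, and so be censored. That works against the stated purpose of these rules, which is to keep patients in the analysis despite incomplete data.

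Month-only dates are foreseeable. Events are asked about by telephone, and Protocol 11.4 tells sites to use relatives, friends or the general physician when patients do not attend.

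**Working it through.** **Inputs.** The two date rules come from SAP 4.3, the limit and censoring rule from SAP 6.2.2.2, and the call window from Protocol 9.1. Uniform timing within months is my assumption.

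**The plan's own limit.** 26 × 7 = 182 and 182 + 7 = 189, as the SAP states.

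**Imputation after death.** With the month known, and the randomization and first-dose dates earlier, the imputed date is the 15th. It falls after death when the event is in the month of death and death is on day 1 to 14. The largest overshoot is 15 − 1 = 14 days.

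- Pairs with event day ≤ death day in a 30-day month: 30 × 31 / 2 = 465.
- Pairs with death on day 1 to 14: 14 × 15 / 2 = 105.
- Share dated after death: 105 / 465 = 22.6%. With the real month lengths of 2017 it is 22.0%.

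That share is conditional on event and death falling in the same calendar month. By interval from event to death, with death days uniform over the year:

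| Event before death | Dated after death |
|---|---|
| same day | 46% |
| 0 to 14 days | 23% |
| 0 to 30 days | 11% |

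Example (assumed dates): randomized 4 September 2017, admitted 2 December (Day 89) but recorded as December 2017, died 6 December (Day 93). The rule gives 15 December (Day 102), 9 days after death. With the death cap it gives 6 December (Day 93).

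**Imputation past Day 189.** This happens when Day 189 falls on day *m* of a month, with *m* from 1 to 14, and the event is in that month.

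- Everyone observed to Day 189: *m* event days are affected. (1 + 2 + … + 14) / 30 = 105 / 30 = 3.5 days, and 3.5 / 189 = 1.9%. A calendar enumeration gives 1.8%.
- Every call made on Day 182: only *m* − 7 observed days remain in that month, for *m* from 8 to 14. (1 + … + 7) / 30 = 28 / 30 = 0.93 days, and 0.93 / 189 = 0.5%.

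The range is therefore about 0.5% to 1.9% of month-only events.

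Example (assumed dates): randomized 25 August 2017, so Day 189 is 2 March 2018. An event on 1 March (Day 188), recorded as March 2018, is imputed to 15 March (Day 202). The patient is censored and the event is lost. With a cap at a call made on 2 March, the event is kept at Day 189.

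**The year-only branch has the same gap.** Randomized 5 July 2017, Day 189 is 10 January 2018. An event known only as 2018 is imputed to 15 January 2018, which is Day 194.

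**On-treatment analysis.** The mechanism is the same at 6 weeks after the last dose. I have not put a figure on it.

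**The case against.** **Month-only dates should be uncommon.** The analysis uses adjudicated events. Protocol 9.4.3.1 sends events to adjudication once critical data are available and queries missing documentation. Protocol 9.6.1.4 requires serious adverse events to be reported within 24 hours of awareness. This stands, and it is why the practical effect is probably small.

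**The medication comparison is selective.** The capped rule is for stop dates; the rule for medication start dates has no death cap either. This also stands. The better comparison is the second sentence of the clinical-outcome rule itself.

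**Discretion and other standards.** SAP 4.3 applies its rules where appropriate, and SAP 4.1 refers to project standards that might add a cap. Those standards are not in the documents, and general discretion does not override an explicit formula.

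**Stronger readings that a reader might infer, which the documents do not support:**

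- That the date is unbounded. It cannot pass the 15th of the reported month, except through the randomization and first-dose lower bounds. A real event is moved; none is invented.
- That the Day 189 loss is peculiar to the month-known rule. The year-only rule shares it; only the missing death cap is specific to the month-known rule.
- That a death cap would restore the timing of the composite. When CV death follows the admission, the capped event falls on the death date, so the composite is timed at death with or without the cap (Day 93 rather than Day 89 in the first example).

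**Conclusion.** The rule is wrong as written, but the point is minor. Two defects follow directly from the text: the month-known branch can date an event up to 14 days after death, and both branches can date an event after the end of follow-up.

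The sizes rest on uniform timing. About 23% of month-only events sharing a 30-day calendar month with the death would be dated after it. About 0.5% to 1.9% of month-only events would be lost past Day 189, depending on when the Week 26 call is made. Both are shares of a number that the documents do not give.

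The effect stays within the descriptive secondary and exploratory time-to-event analyses, which carry no type I error control. A reader should not infer any effect on the MCP-Mod tests of LVEF or NT-proBNP, because they do not use these dates.

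**What to change.** In SAP 4.3:

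1. Add the existing death clause to the month-known sentence.
2. In both branches, cap the imputed date at the earliest of the death date and the last visit or contact date, or the date on which the event was reported if that is captured. State the aim: an event known to have occurred within the follow-up window is not imputed beyond it.
3. Apply the same principle to the on-treatment analysis. There the reporting date matters more. For a patient who takes the last dose the day before a Day 140 visit, the limit is 139 + 42 = Day 181, before the Week 26 call, so a cap at last contact may not bring the event back inside.

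The cost is a clause in each sentence and a small change to the date derivation. Death and last-visit dates are already needed for censoring in SAP 6.2.2.2. The documents do not show that a reporting date is held for each event; if it is not, the last visit or contact date is the workable cap.

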4.3 Handling of Missing Data

All missing or partial data will be presented in the patient data listing as they are recorded in the eCRF.

A number of descriptive analyses will be performed to better understand missing data patterns. The frequency, proportion and the reasons for premature discontinuation of both the study and study treatment will be reported. Kaplan-Meier plots for “time to end of study treatment (calculated as days from first dose to the earliest date of stop medication, including premature stop of study medication and death, for the calculation all the subjects will be considered to have an event-stop of study medication)” and “time to end of study”(calculated from randomization to the earliest date of visit 9, death, and the last visit if subject drops off from study prematurely, for the calculation all the subjects will be considered to have an event-stop of study) will be provided, by treatment group and overall.

The number of patients who prematurely discontinue study participation or intake of study medication will be summarized with respect to the key subgroups, see section 6.4.1. and the reasons for premature discontinuation of study and / or study treatment. If the proportion of patients who withdraw across the dose groups is not fairly balanced, the impact on the primary variables will be further explored. To further explore the missingness pattern with regards to the “missing at random” assumption, the mean of the baseline values of the efficacy variable will be summarized for patients with and without post-baseline observations, by treatment group and overall.

For the analysis of the primary and secondary variables, it cannot necessarily be assumed that data are missing at random. As the choice of primary analysis will be based on assumptions that cannot be verified, the robustness of the results of the primary analysis will be investigated through appropriate sensitivity analyses making different assumptions, in accordance with the EMA “Guideline on missing data in confirmatory clinical trials”. Detail missing data handling are specified in Section 6.2.1.4.

When appropriate, the following rules will be implemented so as not to exclude subjects from statistical analyses due to missing or incomplete data:

- **Date of CHF diagnosis**
For cases where start month and year are reported but day is missing, impute it with the 1st day of month. If the month is not available, this date will not be imputed.
- **Clinical outcomes**

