6.2.2 Secondary efficacy variables and analyses

6.2.2.1 Secondary efficacy variables

Secondary efficacy variables across different domains are:

- Key echocardiographic parameters, measured values and absolute change from baseline at 20 weeks:
 - Left ventricular end-systolic volume (LVESV; mL)
 - Left ventricular end-diastolic volume (LVEDV; mL)
- High sensitivity troponin T (hs-TNT; ng/L), measured values (log transformed) and absolute / relative change from baseline at 20 weeks as a biomarker of myocardial injury
- Time from randomization to clinical outcomes: CV mortality, HF hospitalization and urgent visits for HF (separate and composite)

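### The SAP's date rule for clinical outcomes puts undated events, and most events known only by year, at about day 0, and its month-and-year rule can date an event after death; the effect is confined to descriptive Kaplan-Meier summaries

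*SAP*

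**What the plan says.** SAP 4.3, under Clinical outcomes, has two rules.

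- **Day missing, month and year known:** "impute the maximum of (date of randomization, first date of study medication, 15.month.year".
- **Month also missing, or no date at all:** "For cases where only start year is reported or completely missing, impute the maximum of (date of randomization, first date of study medication, 15.01.year", with the qualifier "but not later than death date if the subject died".

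The qualifier stands only in the second sentence. Neither rule uses the date of the last contact at which the patient was event-free, or of the contact at which the event was first reported. The rule for HF medication stop dates in the same section does use visit and death dates: "impute it as minimum of [(15, month, year) and (last visit date) and (death date".

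The list of rules opens with "When appropriate, the following rules will be implemented so as not to exclude subjects from statistical analyses due to missing or incomplete data". No alternative is given for cases where a rule would not be appropriate. Protocol 10.3.3 leaves incomplete dates to the SAP, so there is no fallback there.

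The dates feed the secondary variable "Time from randomization to clinical outcomes: CV mortality, HF hospitalization and urgent visits for HF (separate and composite" (SAP 6.2.2.1). SAP 6.2.2.2 says that time to adjudicated events "will be described by means of Kaplan-Meier (KM) estimates by treatment group", and "KM estimates for each visit will be tabulated". It adds an on-treatment version running to 6 weeks after the last dose. SAP 6.2.3 uses the same kind of summary for all-cause mortality, non-fatal myocardial infarction and non-fatal stroke.

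**The concern.** Taking a maximum over randomization, first dose and 15 January keeps the event after randomization, but it then returns the earliest admissible date or something close to it. For an event in the calendar year of randomization, 15 January has usually passed already, so the rule gives day 0. The patient may have attended several later visits with no such event recorded, and the imputed date then contradicts the trial's own records.

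Four things follow for the summaries:

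- Early rows of the visit-by-visit Kaplan-Meier tables gain events that happened later.
- In the composite, a later but poorly dated event placed at day 0 displaces an exactly dated first event.
- An off-treatment event moved to first dose counts as on-treatment.
- Under the month-and-year rule, an event early in the month of death can be dated after the death.

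The design gives some route for such dates to arise. A patient who stops drug has an end-of-treatment visit, a safety visit 4 weeks after the last dose, and then only the Week 26 call (Protocol 6.4.1 and 9.1). Protocol 11.4 allows information on deaths and hospitalizations to come from relatives or a general physician.

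**Working it through.** The documents state no figure for this rule, so there is nothing to reproduce. The check applies the rule as written.

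**Inputs from the documents**
- The two rules and the death cap: SAP 4.3.
- Follow-up limit 182 + 7 = 189 days: SAP 6.2.2.2.
- Recruitment 13 months, calendar start not given: Protocol 5.1.
- Post-baseline contacts at Weeks 2, 4, 8, 12, 20, 24 and 26, i.e. days 14, 28, 56, 84, 140, 168 and 182: Protocol 5.1 and 9.1.

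**Assumptions**
- Entry is uniform over the 13 months, with all twelve possible start months tried.
- First dose is on the day of randomization.
- Event day within 1-189 is uniform, front-loaded (Beta(1,2)) or back-loaded (Beta(2,1)).

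**Step 1. No date.** There is no year, so 15 January drops out and only randomization and first dose remain. All such events fall at about day 0.

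**Step 2. Year only.** Imputed day = max(randomization, 15 January of the event year) - randomization. Illustrative dates:
- Randomized 3 Jul 2017, true event 18 Dec 2017 (day 168): imputed day 0.
- Randomized 1 Nov 2017, true event 1 Mar 2018 (day 120): imputed 15 Jan 2018, day 75.
- Randomized 2 Jan 2017, true event 1 Jun 2017 (day 150): imputed day 13.

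*Hand check, entry even over one calendar year, uniform event times.* The mean event day is (1 + 189)/2 = 95, so about 95/365 = 26.0% of events fall in the next calendar year. Patients randomized on 1-14 January (14/365 = 3.8%) go to 15 January. The share at day 0 is about 100 - 26.0 - 3.8 = 70.2%.

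*Simulation, 200,000 events per scenario, 13-month entry, range over the twelve start months:*

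| Event times | Share at day 0 | Dated before last event-free contact | Mean days too early |
|---|---|---|---|
| Uniform | 65.3-72.5% | 82.8-85.1% | 71.7-76.2 |
| Front-loaded | 73.8-80.5% | 77.1-79.2% | 50.5-53.5 |
| Back-loaded | 56.9-64.6% | 88.5-91.0% | 92.4-99.0 |

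Under uniform times, the average share at day 0 over the start months is 70.2%, as in the hand check. The median imputed day is 0 in every scenario.

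**Step 3. Midpoint between bracketing contacts, uniform event times.** For a bracket of width w, the mean absolute error of the midpoint is w/4.
- All contacts attended and the event reported at the next one: 8.1 days (simulated).
- Event-free at Week 12, reported at Week 26: (182 - 84)/4 = 24.5 days. An event in this bracket imputed to day 0 is on average (84 + 182)/2 = 133 days too early.
- No contact before Week 26: 182/4 = 45.5 days. Imputation to day 0 is on average 182/2 = 91 days too early.

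**Step 4. On-treatment window.** A completer's last dose is the day before the Week 20 visit, about day 139. Adding 42 days gives day 181, close to the end of follow-up, so misclassification is hardly possible. A patient whose last dose is on day 28 has a window to day 28 + 42 = 70. A true event on day 140 is off-treatment, but if it is imputed to first dose it counts as on-treatment.

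**Step 5. Month-and-year rule.** For a patient who dies on the 5th, an event on the 2nd of that month with the day missing is dated the 15th, 10 days after death. Nothing in that sentence prevents it.

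**The case against.** The strongest reply concerns reach. The Kaplan-Meier analyses use adjudicated events. Protocol 9.4.3.1 sends an event to the committee once its critical data are available and queries missing documentation. Serious events are reportable within 24 hours of awareness (Protocol 9.6.1.4), and sites must hold source documents (Protocol 11.1). An adjudicated HF hospitalization whose month is unknown, within 26 weeks of follow-up, should be rare. This stands: the documents give no count, and it could be zero.

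The outcomes are also only described. They are excluded from the MCP-Mod analyses (Protocol 10.3.2.3), no test of them is planned, and the rule is the same in every arm. It alters when an event is plotted, not whether it counts by Week 26. This stands too.

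A reader might infer that the rule distorts the 26-week event rates or biases the comparison of doses. The documents do not support either. With little censoring the Week 26 estimate hardly moves, and nothing shows that partial dates would be more common at some doses than at others.

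A reader might also take 8 days as the usual error of the midpoint. It is the best case. The patients most likely to have partial dates are those with gaps in contact, for whom 25 to 45 days is more realistic.

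Finally, a contact with no event recorded does not prove that none had happened. That is a real limit on the replacement. It does not justify a default to day 0, which ignores the contacts altogether.

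**Conclusion.** The concern holds and is minor. Followed as written, the rule sends every undated event, and 57-81% of year-only events (65-73% under uniform event times), to about day 0, often against visit records that say otherwise. The exceptions are year-only events in the calendar year after randomization and those in patients randomized before 15 January; these go to 15 January. The missing death cap in the month-and-year rule looks like a drafting gap, since the next sentence has one.

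The consequences are limited to descriptive Kaplan-Meier summaries of secondary and exploratory outcomes, mainly the early-visit rows, and to the on-treatment analysis for early discontinuers. The shares rest on assumed entry and event-time distributions and on first dose falling on the day of randomization. How many events the rule would touch cannot be determined from the documents.

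**What to change.** Replace the Clinical outcomes rules in SAP 4.3 with one interval rule for every partly or wholly missing event date.

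- **Lower bound:** the latest of randomization, the last contact documented event-free, and the start of the known month or year.
- **Upper bound:** the earliest of the contact first reporting the event, the end of the known month or year, and death.
- **Imputed date:** the midpoint of the two bounds.

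The death cap then covers month-and-year dates as well. If the mid-month rule is kept, add the cap to it.

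The cost is one SAP paragraph and a small programming change, using visit, report and death dates already collected. The drawback is that an event-free contact may occasionally be a false lower bound for an event reported late.

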6.1 Inclusion criteria

Patients must meet all of the following inclusion criteria to be included in the study:

1. Men or women aged 18 years and older
2. Diagnosis of chronic heart failure (CHF), NYHA class II-IV, LVEF \leq 35% assessed by any imaging modality (e.g. echocardiography, cardiac magnetic resonance, cine levocardiography) within 6 months prior to run-in: if several values are available the last assessment of LVEF should be \leq 35%.
3. One of the following (or both),
 - a) Worsening CHF requiring hospitalization or an unscheduled outpatient visit **in the last 3 months**, both requiring initiation or intensification of heart failure therapy and with either:
 - BNP \geq 100 pg/mL or NT-proBNP \geq 400 pg/mL (sinus rhythm) or

- BNP \geq 300 pg/mL or NT-proBNP \geq 1200 pg/mL (atrial fibrillation)

AND/OR

b) at any time **in the past 4 weeks** one of:

- BNP \geq 300 pg/mL or NT-proBNP \geq 1200 pg/mL (sinus rhythm)
- BNP \geq 600 pg/mL or NT-proBNP \geq 2400 pg/mL (atrial fibrillation)

For patients on treatment with angiotensin receptor-neprilysin inhibitors (ARNIs), e.g. Entresto only NT-proBNP values can be used to assess eligibility.

4. Written informed consent signed before any study-specific procedure

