6.1.4 Prior and Concomitant Medications

All non-study medications taken during the study will be coded using the World Health Organization Drug Dictionary (WHO-DD) in its latest version which is specified in the TS domain and the Anatomical Therapeutic Chemical (ATC) classification system. Coding will include the drug class and preferred drug name.

Non-study medications taken during the study will be categorized as prior medications, concomitant medications during the treatment period, and post treatment medications during the safety follow-up.

Prior medications will be defined as a non-study medication with a stop date prior to the first dose of study treatment.

Concomitant medications will be defined as:

- Non-study medications with a start or stop date on or after the date of the first dose of study treatment;
- Non-study medications that started prior to the first dose of study treatment and are ongoing during the treatment period;
- Non-study medications with partial start dates that indicate that the medication could be concomitant in relation to the date of the first dose of study treatment;
- Non-study medications with completely missing start dates, unless their stop dates confirm otherwise (i.e. the stop date is before the first dose of study treatment).

Post treatment medications are defined as non-study medications taken up to 6 weeks after the last study medication intake.

All concomitant medications will be listed, including verbatim descriptions and coded terms, and flags for prior medications. Prior, concomitant, and post treatment medications will be summarized using frequencies of subjects reporting each drug category and preferred drug name. Additionally

- concomitant medications of interest required by the HF guideline, i.e. ACEI/ARB/ARNI, MRA, beta blockers and/or Ivabradine and their combinations
- other medications of interest relevant to the cardiovascular system, i.e. digitalis glycosides, loop and thiazide diuretics, Potassium sparing agents (excluding MRAs), Statins, anticoagulants, antiplatelets, natriuretic peptides, soluble guanylate cyclase stimulators, GLP-1 antagonists, insulins, and SGLT-2 inhibitors,

will be summarized using frequencies of subjects reporting each preferred drug name at baseline and post-baseline. Frequency of subjects who experienced dose increase, dose decrease or no dose change of concomitant medication of interested required in the HF guideline will also be summarized.

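### SAP 4.3 sets no lower limit on a heart-failure drug stop with unknown day, so some on-treatment stops are dated before first dose and some short courses end before they begin

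*SAP*

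**What the plan says.** SAP 4.3 gives these rules for heart-failure drug dates.

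- **Stop, day missing:** where "stop month and year are reported but day is missing, impute it as minimum of [(15, month, year"), the last visit and the death date.
- **Stop, day and month missing:** "the stop date will be imputed as minimum of [(15.12.year) and (last visit date) and (death date").
- **Start, day missing:** where "start month and year are reported but day is missing, impute it with 15th day of month".
- **Start, year only or fully missing:** "impute it as maximum of (15.01.year, randomization").

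The same section floors incomplete clinical-outcome dates at randomization and first study dose. Only the year-only heart-failure start rule has a comparable floor, at randomization. Neither stop rule has one, and neither document adds a check that a stop follows its start.

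SAP 6.1.4 uses the stop date to classify: "Prior medications will be defined as a non-study medication with a stop date prior to the first dose of study treatment". Its protection for incomplete dates covers partial or missing start dates and does not mention partial stop dates. The same section plans baseline and post-baseline summaries of guideline heart-failure drugs, and a table of "Frequency of subjects who experienced dose increase, dose decrease or no dose change" for them.

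**The concern.** An earliest-of rule built only from upper limits can move a stop back past events that must precede it. Two results follow if the rule is applied as written.

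1. A drug taken at baseline and stopped on treatment can be dated as stopped before treatment.
2. A short course, such as a titration step, can be given a negative duration.

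The protocol (8.1.2) asks that background medication be kept stable during treatment, and the SAP 6.1.4 summaries are where a reader would look to see whether it was. A stop wrongly placed before first dose makes background therapy look more settled than it was.

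**Working it through.** No sample size, power or error rate in the plan depends on this rule, so there is no stated figure to reproduce. The check applies the rule as written to calendar dates.

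**Worked cases**

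| Case | True dates | Dates under SAP 4.3 |
|---|---|---|
| 1 | First dose 20 June; drug stopped 26 June, day unknown | Stop 15 June, 5 days before first dose |
| 2 | Known start 18 September; stopped 27 September, day unknown | Stop 15 September, 3 days before start |
| 3 | Start year only, randomized 20 June; stop June, day unknown | Start 20 June, stop 15 June |
| 4 | Start and stop both September, days unknown; death 10 September | Start 15 September, stop 10 September |

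**Frequency: assumptions.** These are not in the documents: randomization equally likely on each day of a 365-day year; true stop equally likely on each later day; month and year known, day unknown; no early death or last visit. Protocol 9.2.2 places first dose at Visit 2 after randomization, so the two are treated as the same day.

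**Post-randomization stops dated before randomization.** Stop and randomization must share a calendar month, with randomization after the 15th. For a month of L days the count is the sum of (L − r) over r = 16 to L, which is (L − 16)(L − 15)/2.

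- L = 31 gives 120, L = 30 gives 105, L = 28 gives 78.
- Year: 7 × 120 + 4 × 105 + 78 = 1,338.
- All same-month post-randomization stops: L(L − 1)/2 per month, so 7 × 465 + 4 × 435 + 378 = 5,373.

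| Denominator | Share misdated |
|---|---|
| Stops in the randomization month | 1,338/5,373 = 24.9% |
| Stops in the first 28 days (365 × 28) | 1,338/10,220 = 13.1% |
| Stops over 140 days of treatment (365 × 140) | 1,338/51,100 = 2.6% |
| Stops over 182 days, to Week 26 (365 × 182) | 1,338/66,430 = 2.0% |

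**The reverse error.** A stop before randomization is dated on or after it when randomization is on or before the 15th: 0 + 1 + … + 14 = 105 per month, 1,260 per year, or 1,260/5,373 = 23.5% of pre-randomization stops in that month. This comes from choosing mid-month. The missing floor does not cause it.

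**Stop before a known start.** A course of D days is affected when it starts after the 15th and ends in the same month, which is L − 15 − D start days per month where positive.

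- D = 3: 7 × 13 + 4 × 12 + 10 = 149 of 365 (40.8%).
- D = 7: 7 × 9 + 4 × 8 + 6 = 101 of 365 (27.7%).
- D = 14: 7 × 2 + 4 × 1 = 18 of 365 (4.9%).
- D = 21 or more: none.

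**The case against.** **The route to the tables is partly inferred.** SAP 4.3 applies its date rules where appropriate. SAP 6.1.4 does not say that classification uses imputed stops, and a drug begun before first dose and continuing into treatment is concomitant by another of its clauses. It also does not say how a dose change is derived. This stands in part: the effect on the dose-change table is conditional. But the prior definition turns on the stop date, and the imputed date is the only complete one supplied.

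**A reader might infer that a whole drug switch moves to before baseline.** The month-only start rule can put the replacement on the 15th as well. But SAP 6.1.4 treats a partial start that could be concomitant as concomitant, and a replacement that continues is concomitant anyway. For the same reason, the prior misclassification needs a known start date.

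**A reader might infer that these tables are the only check on stable background therapy.** They are not. Concomitant medication is recorded at the study visits and safety calls, all concomitant medications are listed with prior flags, and partial dates are listed as recorded. A reader of the listings can spot an error, but the tables remain uncorrected.

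**A reader might take 25% as the overall error rate.** On a 30 × 30 grid of first-dose day and change day, 225 of 900 cells (25%) fall on the wrong side of first dose. That covers only changes in the first-dose month and adds two errors: 120 cells (13.3%) after shown as before, and 105 (11.7%) before shown as after. The second is the cost of any mid-month guess. Stops in later months cannot cross first dose under this rule.

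**Changes just after first dose may be uncommon.** One entry route involves worsening events "both requiring initiation or intensification of heart failure therapy", but that therapy change precedes entry by up to three months and the route is one of two. It makes changes near first dose plausible and does not show that they are frequent. Long-running background drugs also rarely have the short courses that produce negative durations.

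**Conclusion.** The rule is wrong as written, and the consequence is small. It dates some on-treatment stops before first dose and some stops before their own start, while neighbouring rules in the same section carry the floor that this one lacks. Under uniform dates about 25% of day-unknown post-randomization stops in the randomization month are misdated: about 13% of those in the first 28 days and 2.6% of those over 140 days. How many records this means cannot be said, because the documents do not give the frequency of month-only entries.

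Only descriptive outputs are exposed: the prior and concomitant heart-failure drug summaries, and the dose-change summary if it is built from these dates. A reader might infer a threat to the primary result or a bias towards some dose. The documents do not support that: the primary MCP-Mod test, its error rate, power and sample size do not use these dates, and the rule is the same in every arm.

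**What to change.** In SAP 4.3:

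1. Floor every imputed heart-failure drug stop at that drug's own start date. Where the start is itself imputed and falls after death, last visit or a stop settled under item 2, move the start back to the stop, so that the floor never places a stop after death (case 4).
2. When the month with the missing day is the month of first dose, use the Visit 2 medication record, which is taken before randomization.
   - In use at Visit 2: impute the stop as the later of the current SAP date and the first-dose date. Impute any month-only start as no later than the day before first dose.
   - Already stopped by Visit 2: impute the stop as no later than the day before first dose.
   - Not in use at Visit 2 and reported as started later: impute the start as the later of the 15th and the first-dose date.
3. Where Visit 2 status is unclear, query the site before database lock.

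Where Visit 2 status is known, both the 1,338 and the 1,260 misplaced cases above fall to zero by construction. Simply moving the imputed day to month-end would also remove the 1,338, but it would date all 5,373 pre-randomization stops in that month on or after randomization, against 1,260 now.

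The cost is SAP wording, a small derivation change and a few blinded queries.
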